2.1.4.4 Vital signs variables

Vital signs will be assessed according to the defined visit window (see Section 2.5.4).

The following vital signs will be assessed:

- Weight (Kg),
- Systolic blood pressure (mmHg) in sitting position,
- Diastolic blood pressure (mmHg) in sitting position,
- Heart rate (beats/min) in sitting position.

2.1.4.5 Electrocardiogram variables

Not applicable to the study.

2.1.4.6 Hypoglycemia events

Hypoglycemia events will be evaluated during pre-treatment and on-treatment period (see Section 2.1.4).

All reported hypoglycemia events will be classified according to American Diabetes Association (ADA) classification as follows:

- Severe hypoglycemia: an event that 'Required Assistance Because Subject Was Not Capable of Helping Self'.
- **Documented symptomatic hypoglycemia**: an event during which typical symptoms are accompanied by a measured plasma glucose concentration less than 3.9 mmol/L (<70 mg/dL).
- Asymptomatic hypoglycemia: an event with no symptoms of hypoglycemia but a documented measured plasma glucose concentration less than 3.9 mmol/L (<70 mg/dL).

In addition, the following events will be also considered:

- Documented symptomatic hypoglycemia with measured plasma glucose concentration less than 3.0 mmol/L (<54 mg/dL).
- Asymptomatic hypoglycemia with measured plasma glucose concentration less than 3.0 mmol/L (<54 mg/dL).

- Hypoglycemia (symptomatic or asymptomatic) documented by a measured plasma glucose concentration less than 3.9 mmol/L (<70 mg/dL).
- Hypoglycemia (symptomatic or asymptomatic) documented by a measured plasma glucose concentration of <3.9 mmol/L (< 70 mg/dL) and \geq 3.0 mmol/L (\geq 54 mg/dL).
- Hypoglycemia (symptomatic or asymptomatic) documented by a measured plasma glucose concentration less than 3.0 mmol/L (<54 mg/dL).
- Severe and/or symptomatic hypoglycemia documented by plasma glucose concentration less than 3.9 mmol/L (<70 mg/dL).
- Severe and/or symptomatic hypoglycemia documented by plasma glucose concentration less than 3.0 mmol/L (<54 mg/dL).

In addition to anytime of the day (00:00 to 23:59), hypoglycemia events will be evaluated at the following time periods:

- Nocturnal hypoglycemia: any hypoglycemic event that occurs between 00:00 and 05:59.
- Diurnal hypoglycemia: any hypoglycemic event that occurs between 06:00 and 23:59.

Note: CGM values will not be considered for identifying hypoglycemia.

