7 DISCONTINUATION OF STUDY INTERVENTION AND PARTICIPANT DISCONTINUATION/WITHDRAWAL

7.1 DISCONTINUATION OF STUDY INTERVENTION

7.1.1 Definitive discontinuation

The IMP should be continued whenever possible.

In case the IMP is stopped, it should be determined whether the stop can be made temporarily; definitive IMP discontinuation should be a last resort. Any IMP discontinuation must be fully documented in the eCRF. In any case, the participant should remain in the study as long as possible.

Definitive intervention discontinuation is any intervention discontinuation associated with the definitive decision from the Investigator not to re-expose the participant to the IMP at any time during the study, or from the participant not to be re-exposed to the IMP whatever the reason.

List of criteria for permanent treatment discontinuation

The patients may withdraw from treatment with the IMP if they decide to do so, at any time and irrespective of the reason, or this may be the Investigator's decision. All efforts should be made to document the reason(s) for treatment discontinuation and this should be documented in the eCRF.

The patients may withdraw from treatment with IMP in case of the following:

- At patient's own request, ie, withdrawal of the consent for treatment.
- If, in the Investigator's opinion, continuation with the administration of IMP would be detrimental to the patient's well-being.
- At the specific request of the Sponsor.

A patient must withdraw from treatment with IMP in either of the following cases:

- Intercurrent condition that requires discontinuation of IMP.
- Pregnancy in female participants.
- Necessity to use prohibited therapy (see Section 6.5)

Any abnormal laboratory value will be immediately rechecked for confirmation before making a decision of permanent discontinuation of the IMP for the concerned patient.

See the SoA for data to be collected at the time of intervention discontinuation and follow-up and for any further evaluations that need to be completed.

Handling of participants after definitive intervention discontinuation

Participants will be followed-up according to the study procedures specified in this protocol up to the scheduled date of study completion, or up to recovery or stabilization of any AE to be followed-up as specified in this protocol, whichever comes last.

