In addition to the threshold of plasma glucose of less than 3.9 mmol/L (70 mg/dL), documented hypoglycemia with a measured plasma glucose concentration less than 3.0 mmol/L (54 mg/dL) will also be analyzed (20, 24).

Hypoglycemic events will be evaluated regardless the time of onset during the study and time of the day.

In addition, hypoglycemia events will be evaluated at the following time periods defined by time of the day:

- Nocturnal hypoglycemia: any hypoglycemia of the above categories that occurs between 00:00 and 05:59, regardless of whether participant was awake or woke up because of the event.
- Daytime hypoglycemia: any hypoglycemia of the above categories that occurs between 06:00 and 23:59.

Note: CGM values will not be taken into account for the purpose of hypoglycemia.

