9.4.2 Safety analyses

All safety analyses will be performed on the Safety Population.

The summary of safety results will be presented by treatment group.

The baseline value is defined generally as the last available value before randomization.

For all safety data, the observation period will be divided as follows:

- The **pre-treatment** phase is defined as the time from when the patients sign the informed consent to randomization.
- The **on-treatment** phase is defined as the time from the first injection of the open label IMP (included) up to 2 days after the last injection of IMP.
- The **post-treatment** phase is defined as the time after the on-treatment phase until the end of the study (Follow up Visit).

Treatment-emergent AEs (TEAEs) are AEs that developed or worsened or became serious during the on-treatment phase.

Table 8 - Safety analyses

Endpoint		Statistical Analysis Methods		
Second	ary:			
•	Number of participants with AEs	TEAEs, treatment-emergent SAEs, TEAEs leading to death, and TEAEs leading to treatment discontinuation will be summarized by treatment group for the 12-week on-treatment period.		
		All adverse events will be coded to a "preferred term" (PT) and "high-level group term" (HLGT), "high level term" (HLT) and associated primary "system organ class" (SOC) using the version of MedDRA currently in use by the Sponsor at the time of database lock.		
		Adverse event incidence tables will present by SOC (sorted by internationally agreed order), HLGT, HLT and PT sorted in alphabetical order, and for each treatment group, the number (n) and percentage (%) of patients experiencing at least one AE.		
		Multiple occurrences of the same event in the same patient will be counted only once in the tables within a treatment period. The denominator for computation of percentages is the safety population within treatment group.		
•	Number of participants with at least one hypoglycemic event from baseline to Week 12	The number and incidence of patients experiencing at least one hypoglycemic event will be presented per treatment group and type of hypoglycemic event (see Section 8.2.4) and according to time of occurrence (nocturnal [ie, 00:00 to 05:59], any time of day and daytime [ie, 06:00 to 23:59]) during the 12-week on treatment period. The Odds Ratio and its corresponding 95% CI of Toujeo arm over Tresiba arm for each hypoglycemic event (nocturnal and any time of the day) will be estimated by a logistic regression model.		

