2.1.4 Safety endpoints

To address the secondary objective of evaluating the safety of insulin glargine 300 IU/mL in comparison to insulin degludec 100 IU/mL, the following endpoints will be observed

- Number of patients with adverse events (see Section 8.3 of the protocol).
- Number of patients with at least one hypoglycemic event from baseline to Week 12.
- Number of hypoglycemic events per participant-year from baseline to Week 12.

The safety analysis will be based on the reported adverse events (AEs) and other safety information, such as vital signs. The specific safety parameter of interest for insulin treatment is hypoglycemia.

Observation period

For all safety data, the observation period will be divided as follows:

- The pre-treatment phase is defined as the time from when the patients sign the informed consent to first injection of IMP (excluded).
- The on-treatment phase is defined as the time from the first injection of IMP (included) up to 2 days after the last injection of IMP.
- The post-treatment phase is defined as the time after the on-treatment phase until the end of the study (Follow up Visit).

On-study observation period is defined as the time from start of treatment until the end of the study (defined as last protocol planned visit or the resolution/stabilization of all serious adverse events (SAEs) and AEs of specific interest (AESI) as defined in the protocol).

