2.4.5.1 Analyses of hypoglycemia events

Incidence of patients with at least one hypoglycemia event

A frequency table showing the number and % of patients experiencing at least one hypoglycemic event will be presented for any hypoglycemia and for each type of hypoglycemia (see

Section 2.1.4.6), overall and according to time of occurrence (nocturnal [ie, 00:00 to 05:59], for any time of day and daytime [ie, 06:00 to 23:59] during the on-treatment period.

The Odds Ratio and its corresponding 95% CI for the Toujeo arm over the Tresiba arm for each hypoglycemic event (nocturnal and any time of the day) during the on treatment period will be estimated by a logistic regression model adjusted on randomization strata of screening HbA1c.

Number and rate of hypoglycemia event

The number and rate of hypoglycemic events (in patient-year of exposure) will be determined for any hypoglycemia and for each type of hypoglycemic event, overall and according to time of occurrence (nocturnal [ie, 00:00 to 05:59], any time of the day) during the on treatment period and in the pre-treatment period.

For each type of hypoglycemic event during the on treatment period, the rate ratio, and its corresponding 95% CI, for the Toujeo arm over the Tresiba arm will be estimated using an over-dispersed Poisson regression model adjusted on randomization strata of screening HbA1c.

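### Hypoglycemia endpoints run from baseline to Week 12 but are analysed on treatment only, an inconsistency within the protocol that the SAP carries over, so non-serious events after early IMP stop reach no hypoglycemia output

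*SAP*

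**What the plan says.** **Endpoint.** SAP 2.1.4 lists as a safety endpoint "Number of patients with at least one hypoglycemic event from baseline to Week 12", together with an event rate per participant-year over the same interval. Protocol Section 3 (Table 1) has the same two endpoints.

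**Collection.** The schedule in Protocol 1.3 has hypoglycemia recorded throughout the study. For patients who stop IMP for good, Protocol 7.1.1 says: "Participants will be followed-up according to the study procedures specified in this protocol up to the scheduled date of study completion". Protocol 8.2.4 adds: "Hypoglycemic events will be evaluated regardless the time of onset during the study and time of the day".

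**Analysis in the protocol.** Table 8 in Protocol 9.4.2 presents incidence by type and time of occurrence, "any time of day and daytime [ie, 06:00 to 23:59]) during the 12-week on treatment period". It sets the same period for the event rate. The same section ends the on-treatment phase 2 days after the last injection.

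**Analysis in the SAP.** SAP 2.1.4 defines on-treatment as the time "from the first injection of IMP (included) up to 2 days after the last injection of IMP". SAP 2.1.4.6 then states: "Hypoglycemia events will be evaluated during pre-treatment and on-treatment period". Under SAP 2.4.5.1, incidence and its odds ratio are on-treatment. Event counts and rates are given for "any time of the day) during the on treatment period and in the pre-treatment period", and the rate ratio is on-treatment. Appendix A repeats the on-treatment limit. SAP 2.1.4 also defines a later phase ("The post-treatment phase is defined as the time after the on-treatment phase until the end of the study"), but no hypoglycemia output uses it.

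**The concern.** The endpoint names one observation window and the analysis uses a shorter one. For a patient who takes IMP to Week 12 the two coincide: the on-treatment phase then ends at or after Week 12. They separate only for a patient who stops early and stays in the study. From 2 days after the last injection, that patient's hypoglycemia is still recorded but is not summarised.

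Three features make this more than a wording matter.

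- The odds ratio comes from a logistic model adjusted only for the HbA1c stratum. A patient who stops in Week 2 without an event is scored as event-free, whatever is recorded in the following 10 weeks.
- Stopping can follow hypoglycemia. Treatment is open-label, and stopping may be the patient's or the investigator's decision (Protocol 7.1.1). The cut-off may therefore be related to the outcome.
- The efficacy period in SAP 2.1.3 runs to Week 12 regardless of treatment discontinuation. Glucose control and hypoglycemia are thus compared over different periods, and no supportive analysis links them.

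SAP 2.1.4 names hypoglycemia as the safety parameter of particular interest for insulin treatment, so its analysis should match its stated endpoint or explain the difference.

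**Working it through.** **Step 1: place the windows side by side.**

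| Source | Window for hypoglycemia |
|---|---|
| Protocol 3 (Table 1), SAP 2.1.4: endpoint | Baseline to Week 12 |
| Protocol 8.2.4: assessment | Any onset during the study |
| Protocol 1.3 and 7.1.1: collection | Throughout, including after IMP is stopped |
| Protocol 9.4.2 (Table 8): analysis | On-treatment, to last injection + 2 days |
| SAP 2.1.4.6, 2.4.5.1: analysis | The same, plus pre-treatment |
| SAP Appendix A: analysis | The same on-treatment period |

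The split runs between the first three rows and the last three, and both groups contain protocol text. The SAP follows the protocol's statistical section.

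**Step 2: trace an event in a patient who stops early.**

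- Onset up to 2 days after the last injection: counted in incidence and rate.
- Later onset, meeting seriousness criteria: also recorded on the SAE form (Protocol 8.2.4), so it can appear in the SAE listing and the post-treatment AE output of SAP 2.4.5.2, but in no hypoglycemia table.
- Later onset, not serious: recorded on the hypoglycemia form only, with no planned hypoglycemia table or listing. This can include an event needing another person's help, because Protocol 8.2.4 makes severe hypoglycemia an SAE only when SAE criteria are met.

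**Step 3: size the uncovered time.** The plan states no figure on this point to reproduce, and the documents give no IMP discontinuation rate. Inputs:

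- Treatment period T = 84 days (Protocol 1.3).
- Carry-over = 2 days (SAP 2.1.4).
- Share of patients stopping early = d (assumed).
- Stop times uniform over the 84 days, and every patient who stops stays to Week 12 (both assumed).

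Mean uncovered days per patient who stops = (T − 2)² / (2T) = 82² / 168 = 6724 / 168 = 40.0 days.

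Share of planned person-time uncovered = d × 40.0 / 84:

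| d | Uncovered share |
|---|---|
| 2% | 1.0% |
| 5% | 2.4% |
| 10% | 4.8% |
| 22% | 10.5% |

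The 22% is the protocol's assumed CGM non-evaluability rate, used here only as an upper bound.

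**Step 4: vary the timing at d = 5%.**

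- All stop at Week 2: 0.05 × (84 − 14 − 2) / 84 = 0.05 × 68 / 84 = 4.0%.
- All stop at Week 10: 0.05 × (84 − 70 − 2) / 84 = 0.05 × 12 / 84 = 0.7%.

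**Step 5: ask which estimate is exposed.** The rate is per patient-year of exposure, so events and time at risk both stop with treatment. The odds ratio has no such adjustment. It is affected only by patients with no event before their cut-off.

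**The case against.** The strongest reply is that the plan is coherent as it stands. The protocol's statistical section prescribes the on-treatment period for both endpoints, and the SAP applies it. Safety is analysed by treatment actually received, for which an on-treatment window is a normal choice. The sentence in Protocol 8.2.4 comes just before the nocturnal and daytime categories and names no analysis period, population or estimator. SAP 2.4.5 calls the safety analysis essentially descriptive, and hypoglycemia is outside the testing hierarchy, so no confirmatory claim depends on it. Events after stopping occur under other insulins.

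Most of this stands. It rules out three stronger readings that a reader might infer:

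- **That the SAP narrowed the protocol.** Table 8 in Protocol 9.4.2 already has the on-treatment limit.
- **That every event in an early stopper is lost.** Events up to 2 days after the last injection are counted, and serious later ones can reach the SAE or post-treatment AE output.
- **That the arm with more early stops will look safer.** This would need an imbalance in stopping that the documents do not indicate. The exposure-based rate ratio also limits the effect.

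The reply does not remove the mismatch with the endpoint's own window, and it does not supply an output for the non-serious later events. The SAP already defines an on-study period and reports deaths over it, so a wider window is not foreign to the plan.

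**Conclusion.** The point holds in a limited form. The baseline-to-Week 12 endpoint and Protocol 8.2.4 disagree with Table 8 in Protocol 9.4.2, and the SAP inherits the disagreement. As a result, non-serious hypoglycemia more than 2 days after the last injection, in patients who stop IMP but remain to Week 12, is collected and then left out of all planned hypoglycemia output. The incidence odds ratio scores such a patient as event-free if no earlier event occurred.

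With 5% to 10% stopping at uniform times and full retention, the gap is about 2.4% to 4.8% of planned person-time. Lower retention after stopping would shrink it, and earlier stopping would enlarge it. These figures describe missing follow-up. They do not measure a shift in the odds ratio or rate ratio, and the documents do not allow one to be calculated. The effect is probably small unless stopping is frequent or differs between arms. The primary analysis is untouched. The change is worth making because it is cheap and lets the analysis cover the stated endpoint period.

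**What to change.** 1. **Reconcile the wording.** Bring Protocol 8.2.4 and the baseline-to-Week 12 endpoint into line with Protocol 9.4.2 (Table 8), SAP 2.1.4.6, SAP 2.4.5.1 and Appendix A, stating that the main hypoglycemia analysis is on-treatment.
2. **Keep the on-treatment tables** as the main analysis.
3. **Add one supportive analysis to SAP 2.4.5.1**, from first injection to Week 12 regardless of IMP discontinuation. Give incidence, odds ratio, rate and rate ratio, with observed follow-up time as the rate denominator. Restrict it to the main categories, for example severe, documented below 70 mg/dL and documented below 54 mg/dL. Repeating all ten categories in SAP 2.1.4.6 would be out of proportion.
4. **Add a by-arm listing** of post-treatment hypoglycemia.

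The cost is a rerun of existing programs with a different end date and denominator, plus one listing. No new data are needed. The drawback is that the wider window includes events under other insulins after IMP is stopped, so the added analysis should be labelled supportive only.

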4.2 SCIENTIFIC RATIONALE FOR STUDY DESIGN

The fluctuations in blood glucose, regular short-duration periods of hyperglycemia and hypoglycemia, which are not detected by the measurements of HbA1c, may possibly contribute to vascular pathological processes and diabetic complications. This association may be independent of average glucose exposure expressed by HbA1c. This hypothesis remains controversial, but stems from the observation that intensive (versus standard) glucose control in the DCCT was associated with reduced risk for retinopathy after correcting for HbA1c (4). Supportive observations report that the coefficient of variation of FPG independently predicted mortality in T2DM (5). Potential mechanisms that might link oscillating blood glucose with vascular pathology include oxidative stress and inflammatory processes, with enhanced apoptosis of vascular endothelial cells (6).

This is a randomized, active-controlled, 12-week open-label study to compare the efficacy of Toujeo with Tresiba using CGM glucose profiles, sampling ambulatory glucose level every 5-minutes over a 20-day period at Week 12. The CGM during study period will be blinded to both the Investigators and patients.

Eligible patients will be randomized to either Toujeo or Tresiba, both given once-daily by SC injection in the morning. Patients allocated to Toujeo or Tresiba groups will switch from their previous basal insulin. During 4 weeks of the run-in period, patients will be required to titrate their basal and mealtime insulin to optimize the fasting and 2-hour postprandial self-monitoring of plasma glucose (SMPG) targets. The baseline CGM will be performed during the last 3 weeks of run-in.

The primary objective of the study is to explore the percent of time in target CGM glucose range of 70-180 mg/dL with Toujeo versus Tresiba treatment at 12 weeks of treatment. In addition, all hypoglycemia incidence and distribution (24 hours and nocturnal) will be analyzed according to the American Diabetes Association (ADA) classification (severe, documented symptomatic, asymptomatic, probable and relative) (20). Glucose stability and variability will be assessed between and within each group via measurements of glucose CV.

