Before (pre-injection after randomization) and 2 hours after breakfast; lunch; dinner, and at bedtime: at least 1 day during the week that precedes Visits 6 and 18. Note: 7-point SMPG profile should also be pre-injection during the run-in period in cases where the patient's current basal insulin is administered in the morning.

SMPG during symptomatic hypoglycemia

Whenever the patients feel hypoglycemic symptoms, plasma glucose should be measured by the patient (or others, if applicable), if possible. Patients should be instructed to self-assess plasma glucose levels prior to carbohydrate intake/administration of glucose whenever symptomatic hypoglycemia is suspected, unless safety considerations necessitate immediate carbohydrate/glucose rescue prior to confirmation with the SMPG.

Patients have to document hypoglycemic events appropriately in their diaries and contact the Investigator as soon as possible following severe events for review and for decision on any necessary actions to be taken.

All hypoglycemia episodes will be documented on the "hypoglycemia specific form" in the eCRF. This includes all symptomatic hypoglycemia events and asymptomatic hypoglycemia. Investigators should review the SMPG diary entries (and when available also data stored in the glucometer) to assess data for episodes of hypoglycemia, ie, to confirm episodes reported by patients in the diary and also to identify any episodes that were not reported in the diary).

Property of the Sanofi group - strictly confidential

Page 49

Hypoglycemia events fulfilling the criteria of a SAE will also be documented on the AE and SAE form in the eCRF.

Recording of SMPG data

Patients will document their SMPG values with the testing times in the Sponsor-provided diary. If for any reason, SMPG is recorded by the patient in a non-Sponsor provided diary, the Investigator (or designee) and patient will sign/initial the data so that the diary can be kept in the study source documents.

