8.2.4 Hypoglycemia

Hypoglycemia will be reported on the specific hypoglycemia event information form of the e-CRF. Hypoglycemia fulfilling the seriousness criteria will be documented in addition on the SAE form in the e-CRF.

The SMPG values will be used for the confirmation of hypoglycemia (ie, episodes both reported and not-reported by patients in the diary).

Hypoglycemic events will be categorized (20, 22, 23, 24) as follows:

- Severe hypoglycemia: Severe hypoglycemia is an event requiring assistance of another person to actively administer carbohydrate, glucagon, or other resuscitative actions. These episodes may be associated with sufficient neuroglycopenia to induce seizure, unconsciousness or coma. Plasma glucose measurements may not be available during such an event, but neurological recovery attributable to the restoration of plasma glucose to normal is considered sufficient evidence that the event was induced by a low plasma glucose concentration. The definition of severe symptomatic hypoglycemia includes all episodes in which neurological impairment was severe enough to prevent self-treatment and which were thus thought to place participants at risk for injury to themselves or others. Note that "requiring assistance of another person" means that the participant could not help himself or herself. Assisting a participant out of kindness, when assistance is not required, should not be considered a "requiring assistance" incident. Severe hypoglycemia will qualify as an SAE only if it fulfills SAE criteria (see Section 10.3). For example, events of seizure, unconsciousness or coma must be reported as SAEs.
- **Documented symptomatic hypoglycemia:** Documented symptomatic hypoglycemia is an event during which typical symptoms of hypoglycemia are accompanied by a measured plasma glucose concentration less than 3.9 mmol/L (70 mg/dL). Clinical symptoms that are considered to result from a hypoglycemic episode are, eg, increased sweating, nervousness, asthenia/weakness, tremor, dizziness, increased appetite, palpitations, headache, sleep disorder, confusion, seizures, unconsciousness, or coma.
- **Asymptomatic hypoglycemia:** Asymptomatic hypoglycemia is an event not accompanied by typical symptoms of hypoglycemia but with a measured plasma glucose concentration less than 3.9 mmol/L (70 mg/dL).

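### The protocol names five hypoglycemia classes but it and the SAP define only three, so a non-severe symptomatic event without a glucose reading below 70 mg/dL has no class

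*SAP*

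**What the plan says.** Protocol section 4.2 commits to analyzing hypoglycemia, over 24 hours and at night, under an ADA classification with five named classes: "severe, documented symptomatic, asymptomatic, probable and relative". Section 8.2.4 opens its list with "Hypoglycemic events will be categorized (20, 22, 23, 24) as follows" and gives three: severe, documented symptomatic and asymptomatic, with a further cut at 54 mg/dL. Table 8 in section 9.4.2 takes its event types from section 8.2.4.

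SAP section 2.1.4.6 begins "All reported hypoglycemia events will be classified according to American Diabetes Association (ADA) classification as follows" and lists the same three. A severe event is one that "Required Assistance Because Subject Was Not Capable of Helping Self"; no glucose value is needed. A documented symptomatic event is "an event during which typical symptoms are accompanied by a measured plasma glucose concentration less than 3.9 mmol/L (<70 mg/dL". An asymptomatic event needs a reading below the same threshold. Seven further groupings follow, and CGM may not be used to identify events. SAP section 2.4.5.1 tabulates incidence "for any hypoglycemia and for each type of hypoglycemia", does the same for numbers and rates, and adds odds ratios and rate ratios.

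On collection, protocol section 8.1.4 tells patients to measure before taking carbohydrate "unless safety considerations necessitate immediate carbohydrate/glucose rescue prior to confirmation with the SMPG". The same section sends every symptomatic event, as well as asymptomatic ones, to the hypoglycemia form.

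**The concern.** Two classes announced in section 4.2 have no definition and no table row anywhere. They would naturally hold symptomatic events that were not confirmed by a low reading. The protocol foresees some of these, because it lets a patient treat first when safety requires it, and it collects them.

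Hypoglycemia is a secondary safety endpoint, and SAP section 2.1.4 singles it out as the safety parameter of interest for insulin. If reported events have no class, the typed results cover only part of what was reported, and a reader cannot tell how large the remainder is. The trial is open-label and the decision to measure lies with the patient, so the unmeasured share should be visible by arm. The plan does not report it.

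**Working it through.** No figure in the plan needs reproducing; this is a comparison of definitions.

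**Step 1: count the classes.** Protocol 4.2 names 5. Protocol 8.2.4 defines 3. SAP 2.1.4.6 defines 3. The difference is 5 − 3 = 2: probable and relative. Neither document says what those two terms mean, so the check below uses only the SAP's own definitions.

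**Step 2: test two events against every SAP definition.** Event A is symptomatic, not severe, with no glucose value. Event B is symptomatic, not severe, with a value at or above 70 mg/dL. The SAP has 3 classes + 7 groupings = 10 definitions.

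| SAP 2.1.4.6 definition | What it requires | A | B |
|---|---|---|---|
| Severe | Assistance needed | no | no |
| Documented symptomatic | Symptoms and reading <70 | no | no |
| Asymptomatic | No symptoms and reading <70 | no | no |
| Documented symptomatic, lower cut | Symptoms and reading <54 | no | no |
| Asymptomatic, lower cut | No symptoms and reading <54 | no | no |
| Either, below 70 | Reading <70 | no | no |
| Either, 54 to below 70 | Reading ≥54 and <70 | no | no |
| Either, below 54 | Reading <54 | no | no |
| Severe and/or symptomatic, below 70 | Severe, or symptoms with reading <70 | no | no |
| Severe and/or symptomatic, below 54 | Severe, or symptoms with reading <54 | no | no |

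Each event meets 0 of 10. CGM cannot supply the missing value, because the SAP rules it out for this purpose.

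**Step 3: find where A and B can still appear.** The any-hypoglycemia row of SAP 2.4.5.1 covers incidence, number and rate. The SAP does not define that row. The rate ratio is specified for each type of event, so it is unclear whether any hypoglycemia gets one.

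**Step 4: ask what size can be stated.** The documents give no proportion of unmeasured events. As an assumption only, let 5% to 15% of symptomatic events in each arm have no reading, with equal true rates. The documented-symptomatic rate ratio is then (1 − share in Toujeo arm)/(1 − share in Tresiba arm):

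- equal shares: ratio 1.00
- 15% Toujeo, 5% Tresiba: 0.85/0.95 = 0.89
- 5% Toujeo, 15% Tresiba: 0.95/0.85 = 1.12

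The assumed range spans no effect and both directions.

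**The case against.** Section 4.2 is design rationale, and the operative text is consistent: Table 8 points to section 8.2.4, and the SAP reproduces the classes of 8.2.4. On this view the defect is a stale list in one sentence. That stands as an account of how the mismatch arose, and it rules out a charge that the SAP silently dropped classes. SAP section 1.5 lists changes to the protocol's statistical section, which never contained probable or relative events. It does not remove the gap, because the SAP's promise to classify all reported events fails on its own definitions, whatever section 4.2 says.

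Four stronger readings are tempting, and the documents do not support them.

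- **The events are lost.** They are not: on a plain reading the any-hypoglycemia row counts them. Nor is it a fault that the types do not sum to that row, since the SAP's groupings overlap by design.
- **Events that change the IMP dose are left out.** Table 3 speaks of symptomatic episodes, but section 6.6.1.2.2 uses documented symptomatic events and refers to section 8.2.4 for definitions. Whether Table 3 includes unmeasured events is unclear.
- **Fewer events cannot be told from fewer measurements.** Blinded CGM time below 70 mg/dL, all day and at night, is a secondary endpoint with its own ANCOVA (SAP 2.1.3.2 and 2.4.4.2.1). It does not depend on patients choosing to test, although it measures time rather than events.
- **The comparison is biased by about 11%.** The 0.89 above comes only from putting opposite ends of an assumed range in opposite arms. Nothing in the documents shows that measuring differs by arm, or that night-time or urgent episodes go unmeasured more often.

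The documented-symptomatic rate is also not understated as such, because documentation is part of its definition.

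**Conclusion.** The mismatch is certain from the text: five classes announced, three defined, and two kinds of reported event that meet none of ten definitions. The SAP's statement about classifying all reported events therefore cannot be met.

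The consequence is limited to non-severe symptomatic events with no reading, or with none below 70 mg/dL. An event needing assistance is typed as severe without a value, and an event treated first but then measured below 70 mg/dL can still count as documented symptomatic. The primary endpoint, the testing hierarchy, the sample size and the CGM endpoints are untouched, and SAP section 2.4.5 calls the safety analysis essentially descriptive. The number of affected events and any imbalance between arms cannot be derived from the documents. The eCRF is not available either, so it is unconfirmed that symptomatic events with a value at or above 70 mg/dL reach the form. Severity: minor.

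**What to change.** Reconcile protocol sections 4.2 and 8.2.4 with SAP section 2.1.4.6. Then, in SAP sections 2.1.4.6 and 2.4.5.1:

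- Add a separate row for symptomatic events without a glucose value (probable) and, if the form captures them, one for symptomatic events with a value at or above 70 mg/dL (relative). One combined row for symptomatic, not documented events would also do. Write the definitions out, since neither document contains them.
- State that any hypoglycemia means every reported event.
- Report by arm the percentage of symptomatic events without a glucose value.

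If only three classes are intended, correct section 4.2 and still keep one row for unclassified symptomatic events.

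The cost is some wording and a few more descriptive table rows. Section 8.1.4 already sends all symptomatic events to the form. The downside is that one of the added categories is softer than the documented ones, which is why it should be shown separately.
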